The health care resources consumption will take into consideration the following events related to management of COPD and COPD exacerbations: inpatients and outpatients hospitalization (inward and day-hospital), accesses to emergency room, General Practitioner (GP) and outpatient visits, laboratory tests and examinations, pharmacological (LABA, LAMA, SABA, SAMA, ICS/LABA, steroids, antibiotics, long-Term Oxygen Therapy, etc.) and non-pharmacological therapies (pulmonary rehabilitation) occurred/administered during study period.

Medications for adverse events will be considered too.

The annual direct health care resource consumption and related cost will be provided by means of descriptive statistics of the variables mentioned above. In order to describe the health care cost from enrolment up to the end of 12-month follow-up according to the INHS point of view (26), a two steps approach will be followed: (i) first of all the resource consumed since enrolment will be calculated and then (ii) a monetary value will be assigned to the resource consumption.

(i) Health care resources consumption exclusively related to COPD, COPD exacerbations and COPD-drug-related adverse events will be computed during observational period in terms of pharmacological and non-pharmacological treatments, number of (inward and day-hospital) hospitalizations, number of emergency room accesses, number of GP visits, specialist visits, laboratory tests or examinations (spirometry, FEV1, FVC, FEV1 % of the predicted, RV, IC, TLC, DLCO).

(ii) In order to estimate the economic impact on health care sector related cost (30) of the above mentioned health services (hospital admissions, visits, treatments, examinations, spirometry) consumption, a monetary value to each event recorded will be assigned, as defined by the Italian Ministry of Health through the tariffs in force for outpatient setting (31). The cost of hospitalization will be valued according to the most recent available diagnosis-related group (DRG) tariffs (32); finally, pharmacological treatments will be costed at consumer price. All costs will be expressed in €2015. A monthly (or yearly) cost will be provided by taking into account patients according to duration of observation and parametrizing each patient to the 12-month observation period.

Descriptive statistics (mean, standard deviation, median, minimum and maximum) of the annual direct health care resource consumption and related cost will be provided.

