The Morisky medication Adherence Scale 4 items (MMAS-4) is a self-reported, medication-taking behavior scale and consists of four questions about the way patients might experience drug errors or omissions. Each item [F13_MMAS_4.MMAS_4_1 - MMAS_4_4] has a scoring scheme of "Yes" = 0 and "No" = 1. Items are summed to give a non-adherence score ranging from 0 to 4; a higher score means better adherence to therapy (Morisky DE, Green LW, Levine DM. Concurrent and predictive validity of a self-reported measure of medication adherence. *Med Care*. 1986 Jan;24(1):67-74).

The score can be calculated if at least 3 out of 4 of the items are completed. If only one item is omitted, the value for the missing item is the group median of this item that has been completed by all eligible participants. This median value will be imputed for all eligible cases who did not answer this item.

Changes in the MMAS-4 score at each follow-up visit from enrollment will be calculated, for each patient, as the following difference: (score at 6/12 months - score at enrollment), if both scores are available.

COPD pharmacological treatments (classes) ongoing at enrollment

All COPD pharmacological treatments having "End date of therapy" [F20_COPD_PHARMACOLOGICAL_THERAPY.END_DATE_THER] > "Date of enrollment visit" [PatientInfo.Date_enrollment] OR ("End date of therapy" missing and "Ongoing at the end of observation?" [F20_COPD_PHARMACOLOGICAL_THERAPY.ONGOING_THER] = "Yes").

Drug names will be coded by CDM and grouped according to the following categories:

- LAMA alone
- LABA alone

- ICS alone
- LABA + LAMA (Fixed dose combination or not)
- LABA + ICS (Fixed dose combination or not)
- LABA + LAMA + ICS
- SABA or SAMA on demand
- Other: pharmacological therapies for COPD not included in the previous classes.

Categories above are not mutually exclusive: a patient could be classified in more than one category (i.e. if a patient is receiving LABA and SABA on demand, [REDACTED] will be classified both in the “LABA alone” and in the “SABA or SAMA on demand” classes). Only therapies for COPD will be considered (i.e. those records with field Therapy for [F20_COPD PHARMACOLOGICAL THERAPY.THERAPY_FOR] = “COPD”), while therapies for COPD exacerbations or for COPD-related adverse events will not be considered nor classified.

COPD pharmacological treatments (classes) ongoing at 6- and 12-month follow-up visit

At each follow-up visit, all COPD treatments classes (see algorithm above) having

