They will be defined as patients with at least one record in the OXYGEN THERAPY log form with (“Start date of therapy” [F21_OXYGEN_THERAPY.SART_DATE_NF] >= “Date of enrollment visit” [_PatientInfo.Date_enrollment]) OR “Ongoing at the end of observation?” [F21_OXYGEN_THERAPY_ONGOING_NF_THER] = “Yes”.

Patients with adverse events, serious adverse events, and adverse drug reactions

Patients with at least one adverse event (AE) will be those with at least one record in the AEs and ADRs log form with “AE brief description (in English)” [F22_AES_AND_ADRS.AE_DSCRIPT] not missing.

Patients with at least one serious adverse event (SAE) will be those with at least one record in the AEs and ADRs log form with “AE brief description (in English)” not missing AND “Is it a serious AE?” [F22_AES_AND_ADRS.AE_1] = “Yes”.

Patients with at least one adverse drug reaction (ADR) to one of the products marketed by Boheringer Ingelheim (namely: Spiriva Handihaler, Spiriva Respimat, Striverdi Respimat, Spiolto Respimat, Oxivent, Dosberotec, Duorent) will be those with at least one record in the AEs and ADRs log form with “AE brief description (in English)” not missing AND “Is there a reasonable causal relationship with one of the products marketed by Boheringer Ingelheim*?” [F22_AES_AND_ADRS.AE_2] = “Yes”.

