- Absolute and relative frequency of Patients with oxygen therapy during the observational period (see 'Computed variables' chapter)

Percentages will be computed out of the total number of patients evaluable for the FAS.

Table 31. List of oxygen therapies

List of the following variables:

- Patient ID
- "Date of enrollment visit" [[_PatientInfo.Date_enrollment](#)]
- "Kind of therapy" [[F21_OXYGEN_THERAPY.KIND_OF_THER](#)]
- "Drug" [[F21_OXYGEN_THERAPY.DRUG](#)]
- "Flow (L/min)" [[F21_OXYGEN_THERAPY.FLOW](#)]
- "Hours per day" [[F21_OXYGEN_THERAPY.HOURS](#)]
- "Start date of therapy" [[F21_OXYGEN_THERAPY.START_DATE_NF](#)]
- "Ongoing" [[F21_OXYGEN_THERAPY.ONGOING_NF_THER](#)]
- "End date of therapy" [[F21_OXYGEN_THERAPY.END_DATE_NF](#)]
- "Therapy for" [[F21_OXYGEN_THERAPY.NF_THER_FOR](#)]

Only patients evaluable for the FAS will be considered.

Table 32. Patients receiving fixed/non-fixed dose therapies for COPD at enrollment

The table will provide:

- distribution of patients with COPD pharmacological fixed dose therapy at enrollment (see 'Computed variables' chapter);
- distribution of patients with COPD pharmacological non-fixed dose therapy at enrollment (see 'Computed variables' chapter);
- distribution of patients receiving both COPD pharmacological fixed and non-fixed therapy at enrollment (see 'Computed variables' chapter).

Percentages will be computed out of the total number of patients evaluable for the FAS.

Table 33. COPD pharmacological treatments ongoing at enrollment

The table will provide:

- distribution of COPD pharmacological treatments (classes) ongoing at enrollment (see 'Computed variables' chapter).

Percentages will be computed out of the total number of patients evaluable for the FAS.

Table 34. COPD pharmacological treatments ongoing at 6-month follow-up visit

The table will provide:

- distribution of COPD pharmacological treatments (classes) ongoing at 6-month follow-up visit (see 'Computed variables' chapter)

Percentages will be computed out of the total number of patients evaluable for the FAS.

Table 35. COPD pharmacological treatments ongoing at 12-month follow-up visit

The table will provide:

- distribution of COPD pharmacological treatments (classes) ongoing at 12-month follow-up visit (see 'Computed variables' chapter)

Percentages will be computed out of the total number of patients evaluable for the FAS.

Table 36. Medications for adverse events

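### The SAP rule for oxygen therapy in the observation period ignores the end date, so oxygen started before enrolment and stopped during follow-up is not counted in Table 30

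*SAP*

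**What the plan says.** SAP section 3 (Computed variables) sets a patient-level rule for oxygen use: "They will be defined as patients with at least one record in the OXYGEN THERAPY log form with" one of two properties.

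- Limb 1: the start date is on or after the enrolment visit ("F21_OXYGEN_THERAPY.SART_DATE_NF] >=" the enrolment date).
- Limb 2: the flag for therapy ongoing at the end of observation ("F21_OXYGEN_THERAPY_ONGOING_NF_THER") is Yes.

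The oxygen end date appears in neither limb.

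SAP section 4.10, Table 30, reports "Absolute and relative frequency of Patients with oxygen therapy during the observational period" and sets the denominator: "Percentages will be computed out of the total number of patients evaluable for the FAS". Table 31 in the same section lists the oxygen records of FAS patients, including the enrolment date, start date, ongoing flag and end date ("F21_OXYGEN_THERAPY.END_DATE_NF"). It states no date filter.

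For COPD drugs ongoing at enrolment, section 3 does use the end date. A drug qualifies when "F20_COPD_PHARMACOLOGICAL_THERAPY.END_DATE_THER] >" the enrolment date, or when the end date is missing and the ongoing flag is Yes.

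Protocol section 9.7, objective #3, names long-term oxygen among the pharmacological therapies to be described. The same sentence ends with "non-pharmacological therapies (pulmonary rehabilitation) occurred/administered during study period". The section then says that resources consumed from enrolment onwards will be calculated.

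**The concern.** The label of Table 30 promises everyone who used oxygen in the observation period. The rule delivers those who started in the period and those still on oxygen at its end. A patient already on oxygen at enrolment who stopped during follow-up belongs to neither group, yet used oxygen after enrolment and falls within the protocol's scope for objective #3.

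Because the denominator is the whole FAS, such a patient is not set aside as unclassified but is reported as a non-user. Table 30 is the SAP's only summary count of oxygen use, and in a descriptive study the count is the result.

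The planned quality control would not find the problem. SAP section 6 checks the Table 30 output and a random 10% of patients against the algorithm in the SAP, and a program that follows the algorithm faithfully passes.

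**Working it through.** No figure in the plan depends on this rule, so there is nothing to reproduce. The check is whether the rule agrees with actual use in the period.

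**Step 1: date patterns.** Take enrolment as day 0 and the end of observation as day 365. The current rule is: start ≥ 0, or ongoing flag = Yes. True use means that the record overlaps the period. The amended rule adds: or end date > 0.

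| Pattern | Used in period? | Current rule | Amended rule |
|---|---|---|---|
| A. Starts and ends before enrolment | No | Not counted | Not counted |
| B. Starts before enrolment, ends during follow-up | Yes | **Not counted** | Counted |
| C. Starts before enrolment, ongoing at end | Yes | Counted | Counted |
| D. Starts on enrolment day, ends during follow-up | Yes | Counted | Counted |
| E. Starts and ends during follow-up | Yes | Counted | Counted |
| F. Starts during follow-up, ongoing at end | Yes | Counted | Counted |

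The current rule is right for 5 of 6 patterns and the amended rule for 6 of 6. Pattern B is the only failure, and it is a user classed as a non-user, so the error runs downwards only.

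**Step 2: comparison with the drug rule.** Apply the SAP's rule for drugs ongoing at enrolment to a record with the dates of pattern B. The end date is after enrolment, so the record qualifies. The two rules treat the same dates differently, and the SAP gives no reason for the difference.

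**Step 3: incomplete dates.** A tempting alternative is a general overlap rule: start on or before the last observation date, and end date missing, ongoing, or on or after enrolment. It behaves badly in two cases.

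- Start before enrolment, end date missing, flag not Yes: the overlap rule counts the record without evidence of use in the period. The amended rule does not.
- Start date missing, flag Yes: the overlap rule drops the record because its start condition cannot be met. The current and amended rules both count it.

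A last observation date is also not among the variables defined in SAP section 3.

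**Step 4: size.** The documents give neither the prevalence of oxygen use nor a stopping rate. Assume that a share s of the FAS has pattern B and no other qualifying record, so that patients missed = N × s. For N, take 320 (the lower effective sample size in Protocol section 9.5) and 400 (planned enrolment, an upper bound for the FAS).

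- s = 0.5%: 320 × 0.005 = 1.6; 400 × 0.005 = 2.0
- s = 5%: 320 × 0.05 = 16; 400 × 0.05 = 20

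That is about 2 to 20 patients. The percentage in Table 30 would be too low by s itself, 0.5 to 5 percentage points.

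**The case against.** The best defence concerns size. One qualifying record is enough, so a patient whose oxygen was entered again as a new row dated on or after enrolment is still counted. The item collected is long-term oxygen, and patients enter on stable drug treatment with no exacerbation in the previous 3 months, so stopping may be uncommon. Table 31 shows the dates, so a missed record can be found beside Table 30. Oxygen is not named among the correlations of Table 37 or the covariates of Tables 17 to 19, so the effect stops at one descriptive n (%).

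These limits stand, except that how often oxygen is stopped is not established either way. None of them makes the rule correct: no other passage adds pattern B to Table 30, and a listing that shows users whom the summary omits leaves the two outputs inconsistent.

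A reader might also infer that the missed patients are the sicker ones, because oxygen records close at death or withdrawal. The documents do not support this. The flag refers to the end of observation, and section 3 names an End of observation visit apart from the 6- and 12-month visits, so the flag can be read as referring to each patient's own exit. A patient on oxygen at that point could be flagged Yes and counted. Whether sites enter an end date instead depends on the eCRF instructions, which are not in the documents.

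**Conclusion.** The rule is wrong as written. A patient whose only oxygen record starts before enrolment and ends during follow-up is reported in Table 30 as a non-user. This follows from the text alone.

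That Table 30 will in fact be too low is conditional: such patients must exist and have no other qualifying record. The range of about 2 to 20 patients rests wholly on the assumed 0.5% to 5% of the FAS and is not an estimate. Expressing the loss as a fraction of baseline oxygen users would only restate an assumed stopping rate.

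The point touches one descriptive table under secondary objective #3. The primary objective is unaffected. It is worth correcting because the count contradicts its own label and the correction is trivial.

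**What to change.** In SAP section 3, keep both limbs of the oxygen rule and add a third: or the end date of therapy (F21_OXYGEN_THERAPY.END_DATE_NF) is later than the date of the enrolment visit. State that a record starting before enrolment with no end date counts only if the ongoing flag is Yes, in line with the drug rule and with the no-imputation rule in section 4.

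While editing, align the variable names: the rule has "F21_OXYGEN_THERAPY.SART_DATE_NF] >=" and "F21_OXYGEN_THERAPY_ONGOING_NF_THER", whereas Table 31 spells the start date START_DATE_NF and puts a dot before ONGOING_NF_THER.

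Section 3 uses the same construction (ongoing at the end, or started after enrolment) for treatment switching and for numbers of therapies. Those definitions draw on a different form and feed other tables; they should be checked at the same time, but changing them would not correct Table 30.

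The cost is one line of derivation and a rerun of Table 30. All fields are already collected, so neither the eCRF nor the protocol changes.

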4 CONTENTS

The analyses will be performed on the Analysis set specified for each table.

Missing data will not be imputed and so patients with missing data will be excluded from the analyses of that variable(s).

If the investigator is unable to collect the requested information the data will be “NK” (Not Known) or “NA” (Not Available), if the investigator did not record the information the data will be “Not Recorded”.

4.1 Patient disposition

Table 1. Enrolled and evaluable patients

The table will provide absolute and relative frequencies of:

- patients enrolled in the SAT study
- patients evaluable for safety analysis (Safety set) (as described in par. 2.4)
- patients evaluable at enrollment (Full analysis set) (as described in par. 2.1)
- patients evaluable at enrollment and at 6 month follow-up visit (as described in par. 2.2)
- patients evaluable at enrollment and at 12 month follow-up visit (as described in par. 2.3)

The percentages will be computed over the total number of enrolled patients.

Table 2. Reasons for non-eligibility to analyses

The table will describe the reasons for patient non-eligibility.

Absolute and relative frequency distribution will be performed; the percentages will be computed out of the total number of enrolled patients.

Table 3. Premature study termination

The table will describe the distribution of patients withdrawn from the study (“Did the patient complete the study?” [\[F18_STUDY_COMPLETION.SC_1\]](#) = “No”); moreover, absolute and relative frequency of reasons for premature study termination (“Cause of drop out” [\[F18_STUDY_COMPLETION.SC_2\]](#)) will be provided.

Percentages will be computed out of the total number of enrolled patients.

The distribution of patients withdrawn for other reasons will be also reported in a separate table (“If other cause, specify:” ≠ missing [\[F18_STUDY_COMPLETION.SC_3\]](#)), if other reason frequency is >20%.

4.2 Demographics and baseline characteristics

Table 4. Socio-demographic characteristics at enrollment

The table will provide:

- Main descriptive statistics (mean, median, standard deviation, quartiles, min, max) of patients' Age at enrollment ([\[_PatientInfo.Age\]](#))
- Patient distribution by Gender ([\[_PatientInfo.Gender\]](#))
- Patient distribution by Race ([\[F02_SOCIO_DEMOGRAPHICS.SD_Race\]](#))
- Patient distribution by Highest education level at baseline ([\[F02_SOCIO_DEMOGRAPHICS.SD_Education\]](#))
- Patient distribution by Employment status at baseline ([\[F02_SOCIO_DEMOGRAPHICS.SD_Employment\]](#))
- Patient distribution by Housing situation at baseline ([\[F02_SOCIO_DEMOGRAPHICS.SD_Housing\]](#))
- Patient distribution by Marital status at baseline ([\[F02_SOCIO_DEMOGRAPHICS.SD_Marital_status\]](#))

Statistics will be computed out of the total number of FAS patients.

Table 5. Smoke habits at enrollment

The table will provide:

- Patient distribution by Smoking status ([\[F03_LIFE_HABITS.RF_Smoking\]](#))
- Patient distribution by Kind of tobacco ([\[F03_LIFE_HABITS.RF_Kind_Tobacco\]](#))
- Main descriptive statistics (mean, median, standard deviation, quartiles, min, max) of the Estimated amount of tobacco consumed on average (pack/year) ([\[F03_LIFE_HABITS.RF_Estimated_amount_Num\]](#))
- Main descriptive statistics (mean, median, standard deviation, quartiles, min, max) of Smoking duration in years (see 'Computed variables' chapter).

Percentages of smoking status will be computed out of the total number of FAS patients; for Kind of tobacco, Estimated amount of tobacco consumed on average, and Smoking duration, statistics will be computed over the total number of current / former smokers in the FAS.

Table 6. COPD medical history at enrollment

The table will provide:

- Main descriptive statistics (mean, median, standard deviation, quartiles, min, max) of COPD duration at enrollment in years (see 'Computed variables' chapter)
- Main descriptive statistics (mean, median, standard deviation, quartiles, min, max) of age at COPD diagnosis (see 'Computed variables' chapter)
- Frequency distribution of Number of exacerbations in the last year at enrollment (in classes) ([\[F04_COPD_MEDICAL_HISTORY.MH_nr_exacerbations_num\]](#))
- Main descriptive statistics (mean, median, standard deviation, quartiles, min, max) of Number of exacerbations in the last year at enrollment ([\[F04_COPD_MEDICAL_HISTORY.MH_nr_exacerbations_num\]](#))

Descriptives will be computed out of the total number of FAS patients.

Table 7. Comorbidities at enrollment

The table will provide the patient distribution by ongoing Comorbidity(ies) at enrollment (

[\[F06_COMORBIDITIES.COM_Comorbidities\]](#)). A patient could have more than one comorbidity.

Moreover, the patient distribution by Other comorbidities* will be provided.

Percentages will be computed out of the total number of FAS patients .

Table 8. Vital signs at enrollment

The table will provide:

- Main descriptive statistics (mean, median, standard deviation, quartiles, min, max) of patients' Weight at enrollment ([\[F05_PHYSICAL_EXAMINATION.PE_Weight_Num\]](#))
- Main descriptive statistics (mean, median, standard deviation, quartiles, min, max) of patients' Height at enrollment ([\[F05_PHYSICAL_EXAMINATION.PE_Height_Num\]](#))
- Patient distribution by BMI classes (see 'Computed variables' chapter)
- Main descriptive statistics (mean, median, standard deviation, quartiles, min, max) of BMI at enrollment ([\[F05_PHYSICAL_EXAMINATION.PE_BMI\]](#))

Descriptives will be computed out of the total number of FAS patients.

Table 9. Respiratory Functions at enrollment

The table will provide:

- Main descriptive statistics (mean, median, standard deviation, quartiles, min, max) of patients' values of FEV1 (L) at enrollment [F07_FUNCTIONAL_ASSESSMENT.FA_FEV1]
- Main descriptive statistics (mean, median, standard deviation, quartiles, min, max) of patients' values of FEV1 of the predicted (%) at enrollment [F07_FUNCTIONAL_ASSESSMENT.FA_FEV1_predicted]
- Main descriptive statistics (mean, median, standard deviation, quartiles, min, max) of patients' values of FVC (L) at enrollment [F07_FUNCTIONAL_ASSESSMENT.FA_FVC]
- Main descriptive statistics (mean, median, standard deviation, quartiles, min, max) of patients' values of FEV1/FVC (%) at enrollment [F07_FUNCTIONAL_ASSESSMENT.FA_FEV1_FVC]
- Main descriptive statistics (mean, median, standard deviation, quartiles, min, max) of patients' values of Residual Volume (L) at enrollment (F07_FUNCTIONAL_ASSESSMENT.FA_RV_Num)
- Main descriptive statistics (mean, median, standard deviation, quartiles, min, max) of patients' values of Inspiratory capacity (L) at enrollment [F07_FUNCTIONAL_ASSESSMENT.FA_VCIN_Num]
- Main descriptive statistics (mean, median, standard deviation, quartiles, min, max) of patients' values of Total lung capacity (L) at enrollment [F07_FUNCTIONAL_ASSESSMENT.FA_TLC_Num]
- Main descriptive statistics (mean, median, standard deviation, quartiles, min, max) of patients' values of DLCO at enrollment [F07_FUNCTIONAL_ASSESSMENT.FA_DLCO_Num], along with the respective DLCO unit [F07_FUNCTIONAL_ASSESSMENT.FA_DLCO_unit].

Descriptives will be computed out of the total number of FAS patients.

During data analysis, the Biostatistician will evaluate to perform the analyses described above also considering the evaluable patients at 6 months and/or at 12 months, depending on the number of patients of these analysis sets (in case the number of patients for these two analysis sets is relevantly different from the number of FAS patients), in order to understand if a selection bias is present.

